9 SAFETY ASSESSMENTS

Details for safety assessments will be recorded in both the CRF and the patient's source documents. During the study, the Investigator or study site personnel will be responsible for querying and recording AEs and SAEs. Adverse events will be recorded from the start of the initial administration of OCR-002 (Treatment Day 1-T0) until 24 hours Following the Completion of the Last Infusion. Serious adverse events will be recorded from Treatment Day 1-T0 through the remainder of the study period. AEs will be evaluated by the Investigator for severity, seriousness, and relationship to study drug as outlined below. Untoward medical events which occur *after* signature of the informed consent *but before* study drug administration will be recorded as medical history.

9.1 Adverse Events

9.1.1 Adverse Event Definition

An adverse event is any untoward medical occurrence associated with the use of a drug in humans, whether or not considered drug related.

An adverse event:

- can be any unfavorable and unintended sign (including an abnormal laboratory finding), symptom, or disease temporally associated with the use of the medicinal product whether or not considered related to the medicinal product;
- can arise from any use of the drug (e.g., off-label use in combination with another drug) and from any route of administration, formulation, or dose, including an overdose; and/or
- can be any sign or symptom not present at baseline, or if present at baseline, worsens in frequency and/or severity, independent of causal relationship to the investigational product.

9.1.2 Expected Adverse Events (with respect to study drug)

An AE or SAR is considered “expected” if: it is listed in the investigational brochure (IB); or, it is listed at the specificity or severity that has been observed; or, if an IB is not required, it is consistent with the risk information described in the general investigational plan. These adverse events are identified in the Investigator Brochure as possibly associated with the study drug, and therefore would be considered EXPECTED adverse events:

- Tachycardia
- Hypotension
- Dizziness
- Nausea
- Vomiting

- Headache
- Chills
- Somnolence
- Restlessness

Acute liver failure is associated with significant morbidity and mortality. Specifically, acetaminophen ALF carries a 28-30% mortality, while ALI carries a 10% mortality. Given these circumstances, determining drug effect and a causal relationship is particularly difficult. The following is a list of signs and symptoms that are expected to occur in patients with ALF or ALI. **These events will be collected and recorded but will not be reported on an expedited basis (e.g., IND safety report) unless the event otherwise qualifies for expedited reporting.**

System Organ Class/Preferred Term
Blood and Lymphatic System Disorders
Anemia
Leukocytosis
Neutropenia
Thrombocytopenia
Cardiac Disorders
Arrhythmias
Bradycardia
Tachycardia
Endocrine Disorders
Hyperglycemia
Hypoglycemia
Gastrointestinal Disorders
Abdominal Distension
Abdominal Pain
Ascites
Diarrhea
Flatulence
Jaundice
Nausea
Upper gastrointestinal bleeding
Vomiting
General Disorders and Administration Site Conditions
Asthenia
Fatigue
Hypothermia
Malaise
Peripheral edema
Pyrexia
Hepatobiliary Disorders
Ascites
Hepatic encephalopathy
Hepatic failure
Hepatomegaly
Jaundice
Portal hypertension
Infections and Infestations

Bacteremia
Pneumonia
Sinusitis
Upper respiratory tract infection
Urinary tract infection
Investigations
Alanine aminotransferase increased
Aspartate aminotransferase increased
Cardiac murmur
Metabolism and Nutrition Disorders
Anorexia
Hyperglycemia
Hyperkalemia
Hypernatremia
Hyperphosphatemia
Hypervolemia
Hypoalbuminemia
Hypocalcemia
Hypomagnesemia
Nervous System Disorders
Headache
Hepatic Encephalopathy
Hyperreflexia
Memory impairment
Psychiatric Disorders
Insomnia
Renal and Urinary Disorders
Azotemia
Oliguria
Renal failure, acute
Respiratory, Thoracic, and Mediastinal Disorders
Dyspnea
Epistaxis
Pleural effusions
Pulmonary edema
Tachypnea
Skin and Subcutaneous Disorders
Pruritus
Purpura
Vascular Disorders
Gastric hemorrhage
Hematoma
Hypotension

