3.3.2 Rationale for Dose Selection

Ocera Therapeutics, Inc. (Durham, NC) has conducted two clinical trials evaluating safety, tolerability and pharmacokinetics in healthy volunteers (n=48) and stable cirrhotic patients (n=43).

Clinical study OCR-002 HE201 was designed as a randomized, placebo-controlled, dose-ranging study, evaluating doses (i.v. infusion) of 1, 3, 10, 20 and 30g given over 4h, and 30, 40 and 60g given over 24h. Following a single ascending dose phase, a multiple ascending dose phase (5d of consecutive administration) for doses of 1, 3, 10 and 20g given over 4h was assessed. The key findings in this study included:

There were no deaths, SAE or AE discontinuations in the study.

A dose related increase in the incidence and severity of adverse events was observed.

Commonly occurring adverse events that appeared to be related to dose included dizziness, somnolence, headache, nausea/vomiting and tinnitus.

There was no evidence to suggest that AEs increased or new AEs occur with multiple dosing.

With respect to blood pressure, there were no apparent trends from placebo with respect to mean changes from baseline; however at dose levels $\geq 20\text{g}/4\text{h}$, several patients experienced clinically significant orthostatic hypotension.

There appeared to be a dose and exposure related increase in mean heart rate starting at a dose level of $10\text{g}/4\text{h}$ and higher. These effects also persisted for longer periods in the higher dose groups.

20g administered over 4 h was the maximum tolerated dose (MTD), however, doses of $10\text{g}/4\text{h}$ and below were well tolerated.

24h Holter monitor recording identified a dose-related increase in heart rate accompanied by modest effects on ventricular repolarization as measured by QT. These effects should be interpreted with caution in light of the small sample size and higher heart rates observed in this study.

There were no clinically significant abnormal laboratory parameters and no patient had any clinically significant changes in physical examination findings or mean

change in body weight between baseline and follow up.

Doses higher than 10g/4h are associated with adverse effects that may be rate and C_{max} related and are likely associated with the non-linear pharmacokinetic profile of phenylacetate above 10 g.

A slower infusion rate (24hr-infusion) avoids C_{max} related adverse effects while providing similar excretion of PAGN.

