9.1.6 Unexpected Adverse Event or Suspected Adverse Reaction

An AE or SAR is considered “unexpected” if: it is not listed in the investigational brochure (IB); or, it is not listed at the specificity or severity that has been observed; or, if an IB is not required, it is not consistent with the risk information described in the general investigational plan. “Unexpected” also refers to AEs or SARs that are mentioned in the IB as occurring with a class of drugs or as anticipated from the pharmacological properties of the drug, but are not specifically mentioned as occurring with the particular drug under investigation.

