9.5 Review of Serious Adverse Events and Suspected Adverse Reactions

Upon entry of a serious adverse event or suspected adverse reaction in the WebDCUTM system, the system triggers automatic e-mail notification of the SAE/SAR to the Project Manager and the IMM. When the SAE/SAR report has been reviewed and deemed to be adequate, the SAE/SAR is forwarded by the Project Manager to the MSM.

The MSM conducts independent reviews of all SAEs and SARs entered into WebDCUTM. Should the IMM or MSM need additional patient data to conduct his/her review, those data may be accessed on the WebDCUTM. The MSM submits his/her opinion on whether the SAE or SAR was (a) in fact, serious, (b) unexpected, and (c) related (with reasonable possibility) to the study drug within 72 hours of notification of the SAE or SAR. The MSM may contact the site for more information or discussion. Should it be determined that the narrative included in the SAE/SAR needs to be amended or enhanced, the SAE/SAR case report form will be returned electronically to the clinical site investigator for enhancement or amendment. If the Investigator and the MSM believe the SAE or SAR is serious, study drug-related (reasonable possibility, probably or definitely), and unexpected, the SAE or SAR requires expedited reporting. When

there is disagreement between the Investigator and the MSM on one or more of these criteria, the SAE or SAR will be reviewed by the IMM as the arbiter as to expedited reporting.

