9.7.1 Trial Stopping Criteria

An apparent, consistent and persistent evidence of net harm that tends to overwhelm any benefit may allow for premature termination of the study.

Continuing enrollment into each dose level of each cohort will be determined on an ongoing basis and at periodic intervals as outlined in Section 9.7. The SRC will receive a report on all reported AEs and SAEs as well as the individual listings of patient with any specific event of interest. The finding of any unexpected SAEs of Grade 3 that are considered not related to acute liver failure in 2 or more patients within a given dose level or of Grade 4 or higher in one patient will lead to suspension of recruitment and review of the complete data by the MSM. Following the MSM's review, the safety report (and any comments from the MSM) will be sent to the SRC. The SRC will make the final recommendation for early termination versus continuation of the study after reviewing the available data. The decision will be guided by safety.

If the SRC does not stop the trial, the trial will proceed with enrollment as outlined in section 9.7 for Cohorts 1 and 2. In addition to the planned evaluations, the MSM and SRC will receive

quarterly safety summary reports of enrollment, baseline demographics, withdrawals from treatment and all AEs and SAEs with information on relation to study treatment.

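### Sections 9.1.2 and 9.1.6 are not complements: a reaction listed in the Investigator's Brochure but seen at an unlisted severity is both expected and unexpected, and no rule says which prevails.

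*Combined protocol and SAP*

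**What the plan says.** **Definitions.** Section 9.1.2 makes an event expected if "it is listed in the investigational brochure (IB); or, it is listed at the specificity or severity that has been observed". A third limb covers the case where no IB is required. The section then names nine drug reactions (tachycardia, hypotension, dizziness, nausea, vomiting, headache, chills, somnolence, restlessness), without grades, as "identified in the Investigator Brochure as possibly associated with the study drug, and therefore would be considered EXPECTED adverse events". Section 9.1.6 makes an event unexpected if "it is not listed in the investigational brochure (IB); or, it is not listed at the specificity or severity that has been observed", again with a limb for no IB. It adds that reactions the IB attributes only to a drug class, or only anticipates from pharmacology, are unexpected.

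**Where the label is used.**
- Section 9.5: if the investigator and the Medical Safety Monitor (MSM) consider an event serious, drug-related "and unexpected, the SAE or SAR requires expedited reporting".
- Section 9.7.1: recruitment is suspended on "The finding of any unexpected SAEs of Grade 3 that are considered not related to acute liver failure in 2 or more patients" within a dose level, or on Grade 4 or higher in one patient.
- Synopsis, Safety Analysis: expectedness is to be summarised by cohort. Section 11.7.1 does not repeat this.

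**A rule that does not use the label.** The Treatment section of the synopsis stops dose escalation (Dose Levels 1 to 3) or continued administration (Dose Level 4) after Grade 3 SAEs in two or more patients of a dose level, or one SAE of Grade 4 or higher, when not attributed to acute liver failure (ALF). Expectedness plays no part in it.

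**The concern.** The opposite of *not listed, or not listed at this severity* is *listed, and listed at this severity*. Section 9.1.2 keeps the *or*, so listing alone is enough to make an event expected, and its sentence on the nine ungraded terms applies the definition in just that way.

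The state in conflict is a foreseeable one. Section 3.3.2 reports that adverse events rose with dose in both frequency and severity in the study it summarises, and says of SAEs: "There were no deaths, SAE or AE discontinuations in the study". Section 3.3.2 also presents this trial as the first use of the drug in ALF. A known reaction appearing in a more severe form is therefore a signal the safety plan should be able to classify. With two definitions in force, two sites could label the same event differently, and with it the expedited report, the 9.7.1 suspension and the expectedness table.

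**Working it through.** The plan gives no figure to reproduce; the check is one of logic.

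**Inputs.** Let L = the term is listed in the IB, and S = it is listed at the observed specificity and severity. S implies L, because an event cannot be listed at a severity without being listed. An IB exists (section 3.2 refers to it), so the no-IB limb of each definition is inactive. The drug-class sentence in 9.1.6 is left aside here.

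**Formulas.**
- 9.1.2: expected = L or S. Since S implies L, this reduces to L; the severity test adds nothing.
- 9.1.6: unexpected = (not L) or (not S). Since not L implies not S, this reduces to not S.
- Complement of 9.1.6: expected = L and S, which reduces to S.

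**The three possible states.**

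| State | Expected under 9.1.2 | Unexpected under 9.1.6 | In both | Expected if joined by *and* |
|---|---|---|---|---|
| Listed, at the observed severity | yes | no | no | yes |
| Listed, not at the observed severity | yes | yes | **yes** | no |
| Not listed | no | yes | no | no |

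As written, one state of three falls into both classes. With *and*, none falls into both and none into neither.

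**Example.** Two patients in one dose level have serious Grade 3 hypotension, judged drug-related and not due to ALF. Assume the IB lists hypotension, but not at that severity.

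| Rule | Reviewer applies 9.1.2 | Reviewer applies 9.1.6 |
|---|---|---|
| Expedited report (9.5) | condition not met | condition met |
| Recruitment suspension (9.7.1) | condition not met | condition met |
| Stop rule (synopsis, Treatment) | met | met |

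The choice of definition changes the first two rows and leaves the third as it is. The table also shows that the synopsis and 9.7.1 differ on whether expectedness matters at all for the same count of events, although section 5.2 sends the reader to 9.7 for escalation and stopping criteria.

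**The case against.** **The rules use the word *unexpected*, which 9.1.6 defines.** Neither 9.5 nor 9.7.1 exempts an event because it also meets 9.1.2. On a literal reading, meeting 9.1.6 is enough. This stands in part: a missed report is possible, not compelled. But 9.1.2 is also in force and says in terms that its nine reactions are to be considered expected, so a reviewer who relied on it would be following the protocol.

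**Independent review continues.** "The MSM conducts independent reviews of all SAEs and SARs entered into WebDCUTM", including whether each is unexpected. If the investigator and the MSM disagree, "the SAE or SAR will be reviewed by the IMM as the arbiter as to expedited reporting". The Safety Review Committee (SRC) reviews safety after each dose level in each cohort and receives all AEs and SAEs, whatever the label (9.7, 9.7.1, 11.5). This limits the harm without removing the conflict. The MSM works from the same two definitions, and the Internal Medical Monitor (IMM) arbitrates only on disagreement; if both readers apply 9.1.2, there is nothing to arbitrate.

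**A reader might infer that a severe listed reaction could pass with no brake at all.** The documents do not support that. The synopsis stop rule has no expectedness condition and would act in the example above.

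**A reader might infer that all nine drug terms are in conflict.** That would need the IB's severity wording, which is not in the documents. The absence of SAEs in one study does not settle it, because seriousness is not severity and section 3.3.2 mentions other studies. Nine is a maximum.

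**A reader might infer that the table of ALF and acute liver injury (ALI) events in 9.1.2 makes those events expected for every purpose.** Five of the nine drug terms (tachycardia, hypotension, nausea, vomiting, headache) do appear in it. But the table is introduced separately as disease-related, it keeps expedited reporting open for events that qualify on other grounds, and 9.7.1 has its own condition on relation to ALF. The overlap is mainly a matter of layout.

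**Conclusion.** The two definitions conflict in exactly one state: listed in the IB, but not at the observed specificity or severity. No section ranks one definition above the other. The number of drug terms exposed lies between none and nine, depending on an IB that the documents do not reproduce.

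The consequence is confined to three things: the expedited report under 9.5, the recruitment suspension under 9.7.1, and the expectedness summary promised in the synopsis. Either of the first two could be omitted if the reviewers apply 9.1.2; neither omission is certain. MSM, IMM and SRC review and the synopsis stop rule operate under either reading.

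This is an internal inconsistency of moderate weight. It deserves correction because safety is the primary objective and the label governs two safety actions, but the documents do not show a trial without safeguards. The conclusion assumes that the no-IB limb is inactive and that *specificity or severity* in 9.1.6 means failing on either one is enough.

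**What to change.** 1. Reword 9.1.2 so that an event is expected only if it is not unexpected under 9.1.6: listed in the IB, and listed at the specificity and severity observed; or, where no IB is required, in line with the risks set out in the general investigational plan. Tying the definition to 9.1.6 keeps the no-IB limb and the drug-class sentence, which a bare change from *or* to *and* would leave unaddressed.
2. State that the nine named reactions are expected only on that condition.
3. Reconcile the synopsis stop rule with 9.7.1 on whether expectedness is a condition.
4. Optionally, give the ALF/ALI event table its own heading and state that it does not define *expected* for 9.5 or 9.7.1.

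The cost is a sentence or two of protocol text, the reconciliation in item 3 and perhaps a heading. In operation, expect a few more expedited reports or suspension reviews.

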9.1.3 Other Adverse Events

In the STOP-ALF Trial, any medical conditions not present prior to the start of the initial study drug infusion but that emerge after the start of the initial study drug infusion are considered AEs. Each AE is a unique representation of a specific event used for medical documentation and scientific analysis. Adverse Events encountered from Treatment Day 1-T0 through 24 hours Following the Completion of the Last Infusion will be recorded, and Serious Adverse Events from Treatment Day 1-T0 through the Day 30 post treatment period will be recorded. Specific clarifications for reporting other events are provided below.

Pre-existing medical conditions or unchanged, chronic medical conditions

All medical conditions present upon arrival to the hospital and prior to the start of the initial study infusion are considered pre-existing conditions and are part of the patient's medical history. Those events that manifest with the same severity, frequency, or duration subsequent to study drug administration need not be recorded as adverse events. These medical conditions should be documented adequately on the medical history and/or physical examination CRFs.

Pre-existing medical conditions or unchanged, chronic medical conditions consistent with natural disease progression are NOT considered AEs unless the pre-existing medical condition is judged by the Investigator to have worsened in severity or frequency or changed in character.

Exacerbation of Pre-existing medical conditions

A pre-existing medical condition judged by the Investigator to have worsened in severity or frequency or changed in character is considered an adverse event and reported through 24 hours Following the Completion of the Last Infusion. If the judgment is that it is a serious adverse event, it is reported through the Day 30 post treatment period.

Lab Abnormalities

If a clinically significant lab abnormality is considered an expected manifestation of the pre-existing disease, it may not require AE reporting if it does not indicate treatment-emergent worsening or new evolution of a medical condition.

Treatment-emergent laboratory abnormalities (e.g., clinical chemistry, hematology, urinalysis), or other investigational studies (e.g., ECGs, X-rays) independent of an underlying medical condition that (a) require medical or surgical intervention or (b) lead to investigational medicinal product interruption or discontinuation **must be recorded as AEs**. If a new laboratory abnormality, ECG or radiographic finding is associated with new signs and/or symptoms (clinical manifestations) an AE should be recorded, either reflective of the abnormality based on the specific investigation(s) or the overall medical condition which is the etiology of that abnormality.

9.1.4 Adverse Reaction

An adverse reaction is any adverse event caused by a drug.

9.1.5 Suspected Adverse Reaction

A Suspected Adverse Reaction (SAR) is any adverse event for which there is a reasonable possibility that the drug caused the adverse event.

For purposes of IND safety reporting, "reasonable possibility" means there is evidence to suggest a causal relationship between the drug and the adverse event. A SAR implies a lesser degree of certainty about the causality than an adverse reaction where the adverse event is caused by the drug.

Suspected adverse reactions are a subset of all adverse events for which there is a "reasonable possibility" that the drug caused the event. A "reasonable possibility" exists if there is evidence to suggest a causal relationship between the drug and the adverse event, such as:

- *A single occurrence* of an event that is uncommon and known to be strongly associated with drug exposure (e.g., angioedema, blood dyscrasias, rhabdomyolysis, Stevens-Johnson Syndrome, anaphylaxis)
- *One or more occurrences of an event* that is not commonly associated with drug exposure, but is otherwise uncommon in the population exposed to the drug (e.g., tendon rupture)
- *An aggregate analysis of specific events* observed in a clinical trial (such as known consequences of the underlying disease or condition under investigation or other events that commonly occur in the study population independent of drug therapy) that indicates those events occur more frequently in the drug treatment group than in a concurrent or historical control group.

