4 OBJECTIVES AND ENDPOINTS

4.1 *Objectives*

4.1.1 **Primary Objective**

To evaluate the safety and tolerability of OCR-002 in patients with acute liver failure/severe acute liver injury.

Hypothesis: Treatment with OCR-002 is safe and tolerable in patients with acute liver failure/acute liver injury.

4.1.2 **Secondary Objectives**

To evaluate the steady state pharmacokinetic and pharmacodynamic profile of OCR-002 in patients with impaired and minimal renal dysfunction using urinary PAGN as a surrogate marker.

Hypothesis: A dose of 10-20g/24h (0.42-.83g/h) will achieve steady state plasma concentrations within 6-12h with little additional accumulation in the ALI/ALF setting.

To evaluate the effect of OCR-002 on ammonia levels in patients with acute liver failure/severe acute liver injury.

Hypothesis: Treatment with OCR-002 will reduce ammonia levels in patients with ALI/ALF.

To evaluate the effect of OCR-002 on neurological function in patients with acute liver failure/severe acute liver injury.

Hypothesis: Treatment with OCR-002 will improve neurological function in patients with acute liver failure/severe acute liver injury.

4.2 *Endpoints*

4.2.1 **Safety Endpoints**

Safety assessments will include: abbreviated physical examinations, vital signs (blood pressure, pulse rate, respiration rate, and body temperature), clinical laboratory tests (hematology and serum chemistry), 12-lead ECGs, and reported and observed adverse events.

4.2.2 **Exploratory Efficacy Endpoints**

- Ammonia concentrations.
- Neurological assessment will be measured by the Glasgow Coma Scale, the West Haven Criteria, and the Orientation log (O-log) (34).

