5 INVESTIGATIONAL PLAN

5.1 *Study Design*

This is a Phase 2a, multi-center, open-label study, conducted in two cohorts in patients

diagnosed with acute liver failure/severe acute liver injury (ALF/ALI) who meet inclusion/exclusion criteria. The acetaminophen adduct assay will be used as an additional test for equivocal or presumed cases of acetaminophen toxicity, where the history is not substantiated and the assay for acetaminophen itself proves to be negative.

Up to 36 evaluable patients are planned to be enrolled in two cohorts:

Cohort 1 will include patients with ALF/ALI with minimal renal dysfunction at the time of enrollment (defined as serum creatinine ≤ 1.5 mg/dL and mean arterial pressure of >65 mmHg).

Cohort 2 will include patients with ALF/ALI with compromised renal function (defined as a serum creatinine >1.5 mg/dL and <10 mg/dL) and mean arterial pressure of >65 mmHg.

Informed consent will be obtained from the patient and/or patient's legally authorized representative or family member [as defined in 21CFR50.3(m)]. All patients will receive medical care for acute liver failure/severe acute liver injury according to the institution's standards of care. Standard of care may include, but is not limited to, administration of NAC and consideration for orthotopic liver transplantation. All patients in Cohort 2 with a serum Cr level of ≥ 2.0 will be considered for placement on continuous veno-venous hemodialysis (CVVHD) for an appropriate interval as standard of care for this condition.

The initial dose of OCR-002 will be initiated once consent is obtained, all eligibility criteria are confirmed to be met and all baseline measurements have been completed. The infusion may begin after obtaining signed informed consent; or, up to 32 h after obtaining consent should the time be necessary to complete any pre-study drug initiation requirements and/or to provide a time frame for study drug administration.

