6 PATIENT POPULATION

6.1 Number of Sites and Patients

The study will be conducted at between 6 to 12 centers in the US that are experienced, high-volume sites in the ALF Study Group. All patients enrolled in the therapy trial will have been enrolled in the ALFSG registry. Up to 36 evaluable male and female patients aged 18 to 65 years with ALI/ALF will be enrolled into two cohorts. Each patient may participate in only one cohort. For each patient, the study duration will be approximately 32 days, including Screening, Baseline, up to 5 days of treatment, the Completion of the Last Infusion, a 24 hours Following the Completion of the Last Infusion, and a post treatment period on Day 30 (approximately 30 days after Treatment Day 1-T0 unless terminated early from the trial).

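### Section 11 pools ALF and ALI patients in its safety summaries, so counts of deaths and disease-like SAEs cannot be read against background risk

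*Combined protocol and SAP*

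**What the plan says.** The primary hypothesis in Section 4.1.1 is: "Treatment with OCR-002 is safe and tolerable in patients with acute liver failure/acute liver injury". There is no control arm; Section 5.1 describes the trial as follows: "This is a Phase 2a, multi-center, open-label study, conducted in two cohorts". The cohorts are defined by serum creatinine. Section 6.2.1 admits both ALF patients (with encephalopathy) and ALI patients (without), and sets no quota for either.

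Section 9.1.2 gives background mortality: "acetaminophen ALF carries a 28-30% mortality, while ALI carries a 10% mortality". It adds that in this setting "determining drug effect and a causal relationship is particularly difficult", and it lists many events that the disease is expected to produce, among them hepatic failure, encephalopathy, acute renal failure and hypotension.

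Section 9.1.5 gives three examples of evidence for a suspected adverse reaction. Two concern uncommon events. The third, for known consequences of the disease, is an aggregate analysis indicating that "those events occur more frequently in the drug treatment group than in a concurrent or historical control group".

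Sections 11.2, 11.6 and 11.7.1 plan descriptive summaries overall and by renal cohort. The quarterly safety reports in Section 11.5 add a split by site. Section 11.4 makes the per-protocol set primary for all outcomes, with the ITT set as a sensitivity analysis. It also defines a safety population, but Section 11 never says which table uses it. The closing memorandum confirms that no separate SAP exists.

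**The concern.** Death and the other grave events listed in Section 9.1.2 will occur in this trial whether or not the drug does harm. Their counts mean something only beside the risk that the enrolled patients carried at entry. On the protocol's own figures, the strongest stated determinant of that risk is whether the patient had ALF or ALI, and the planned tables do not show it. They split by renal function, for which the protocol gives no background mortality.

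The primary analysis set adds to the difficulty. A patient who dies or is transplanted before 72 h is not in the per-protocol set, so the primary table omits some of the events that matter most.

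At stake is the reading of the primary objective for the gravest outcomes, both in the final report and during the trial. Section 9.7.1 says: "An apparent, consistent and persistent evidence of net harm that tends to overwhelm any benefit may allow for premature termination of the study". It attaches no reference rate to that statement. Without the split, the reading falls back on case-by-case attribution, which Section 9.1.2 calls difficult.

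**Working it through.** **Inputs**
- Evaluable target 36, 25% expected non-evaluable, up to 50 enrolled (synopsis, Study Design).
- Enrolment requires that the infusion has started (Section 6.3.2), so up to 50 patients are treated.
- Mortality: acetaminophen ALF 28-30%, ALI 10% (Section 9.1.2), with no time horizon.
- ALF share *f*: not in the documents. Assumption, shown over 0 to 100%.

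**Step 1. The plan's own figure.** 36 / (1 − 0.25) = 48, against a stated maximum of 50. This reproduces to within 2 patients. The check below uses 50, because a count of deaths should include everyone treated.

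**Step 2. The gap between the two conditions.** 28/10 = 2.8 and 30/10 = 3.0, so stated mortality differs 2.8- to 3-fold.

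**Step 3. Expected deaths with no drug effect.** E = 50 × [*f* × p(ALF) + (1 − *f*) × 0.10]. The last column is the binomial probability of 10 or more deaths at the pooled rate, with p(ALF) = 30%.

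| ALF share *f* | Expected deaths, p(ALF) 28% to 30% | P(10 or more deaths) |
|---|---|---|
| 0% | 5.0 | 0.025 |
| 25% | 7.3 to 7.5 | 0.21 |
| 50% | 9.5 to 10.0 | 0.56 |
| 75% | 11.8 to 12.5 | 0.84 |
| 100% | 14.0 to 15.0 | 0.96 |

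At the midpoint of 29% with all patients ALF, E = 50 × 0.29 = 14.5 and P(10 or more) = 0.945. The binomial is exact in the first and last rows and approximate between them.

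**Step 4. Reading one count.** Ten deaths in 50 is 20%, Clopper-Pearson 95% CI 10.0% to 33.7%. Against an all-ALI background this is twice the expected number. Against an all-ALF background it is 10/14.5 = 69% of expected. The planned tables would not show which background applies.

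**Step 5. What the split can and cannot achieve.** Suppose the mix were known and an exact one-sided rule at 0.025 were applied to 50 patients. Against 10%, the rule flags at 10 or more deaths and has 56% power for a true 20%. Against 20%, it flags at 17 or more (actual level 0.014) and has 32% power for a true 30%. In one renal cohort of 18, power for 20% against 10% is 13%. Knowing the mix makes a count readable; it does not make the trial able to show safety.

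**The case against.** The plan has a fair defence. It calls itself an exploratory pilot, not powered for significance, with descriptive statistics only. ALF/ALI status can be recovered at analysis from encephalopathy and INR at entry, adverse events are listed by patient, and the Safety Review Committee may ask for more data. All of this stands. It makes the gap a missing pre-specified table, and not a loss of information. It does not remove the point, because a descriptive table still has to be split on the factor that drives the outcome, and a split chosen after the deaths are known carries less weight.

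A reader might infer three stronger things that the documents do not support.

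- *That Section 9.1.5 imposes a control comparison which Section 11 then breaches.* It does not. The text is a definition for IND safety reporting, and the comparison stands in a list introduced thus: "A 'reasonable possibility' exists if there is evidence to suggest a causal relationship between the drug and the adverse event, such as". It is one illustration of evidence and not an analysis rule.
- *That the trial's deaths and SAEs can say nothing about safety.* The other two examples in Section 9.1.5 allow a signal from one or a few uncommon events. Every SAE is also judged by the investigator and reviewed independently by the Medical Safety Monitor, and the Internal Medical Monitor arbitrates disagreement on expedited reporting (Sections 9.4 and 9.5). The point is limited to deaths and disease-like SAEs.
- *That a count among the 36 evaluable patients would support opposite conclusions.* Seven deaths in 36 has an exact 95% CI of 8.2% to 36.0%, which contains 10%, 19.5% (an equal mix at 29% and 10%) and 29%. The 36 also exclude patients treated for less than 72 h, so whole-population mortality should not be applied to them.

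The benchmarks have limits too. The 28-30% covers acetaminophen ALF only, while hepatitis A and B, drug-induced, autoimmune and indeterminate cases are eligible. Neither rate has a time horizon to set against Day 30. No background rates are given for SAEs other than death.

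**Conclusion.** The point holds in limited form. As written, Section 11 would report deaths and disease-like SAEs in a way that cannot be set against background risk. It pools two conditions whose stated mortality differs 2.8- to 3-fold, and its primary set omits patients who die or are transplanted before 72 h. In 50 treated patients, expected deaths with no drug effect range from 5.0 to about 14.5. Ten deaths would have a chance of 0.025 or less of being matched or exceeded by background alone only at the all-ALI end; at the all-ALF end that chance is about 0.95.

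The size rests on three assumptions: an ALF share anywhere from 0 to 100% (the two ends are extremes, and a real mix will lie between them), the Section 9.1.2 rates applied to all causes and to the Day 30 window, and the planned maximum of 50 treated. The need for the split does not depend on the exact values. Signals from uncommon events and case-level review are unaffected.

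**What to change.** 1. In Sections 11.2 and 11.7.1, add ALF versus ALI at entry as a pre-specified split, classified from the last encephalopathy grade and INR before the infusion starts. Tabulate death, transplant and SAEs through Day 30 for each group, with exact 95% intervals.
2. State that this table uses all treated patients and not only the per-protocol set.
3. Give the Safety Review Committee the same table in its dose-level and quarterly reports.
4. The Section 9.1.2 rates may stand beside the table as context only, with a note that the ALF figure is for acetaminophen cases and that no time horizon is given.

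This costs SAP text and a little programming. Entry status and SAEs to Day 30 are already collected. The synopsis says that clinical outcomes are recorded, but the team should confirm that the CRF captures a transplant that takes place after the infusion has ended.

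Optional: a descriptive reference group from the registry. Section 6.1 says "All patients enrolled in the therapy trial will have been enrolled in the ALFSG registry", so a link exists. Such a group would need the trial's full eligibility criteria, including ammonia, mean arterial pressure and the exclusions. It would also need an aligned time zero, because trial patients must survive to the start of infusion, up to 32 h after consent. The documents do not say what the registry records, so the cost of this part is unknown, and the comparison would remain non-randomised.
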